STATISTICAL ANALYSIS PLAN

PROTOCOL NUMBER: CPN-302

A Multicenter, Randomized, Double-Masked, Placebo-Controlled, Parallel-Group Study to Evaluate the Efficacy and Safety of APP13007 for the Treatment of Inflammation and Pain after Cataract Surgery, Including a Corneal Endothelial Cell Sub-study

Version No. Final 1.1

Version Date 31 March 2022

APPROVAL SIGNATURE PAGE

Approved by [REDACTED]

Prepared By: [REDACTED]

Date: 31 March 2022

Printed Name: [REDACTED]

Title: Biostatistician

Approved By: [REDACTED]

Date: 31 March 2022

Printed Name: [REDACTED]

Title: Chief Medical Officer

Approved By: [REDACTED]

Date: 31 February 2022

Printed Name: [REDACTED]

Title: Chief Development Officer

SUMMARY OF CHANGES IN SAP AMENDMENT 1

- Clarified Study Day calculation corresponding to Surgery Day 0 and Screening Visit (Day -28 to Day -1) nomenclature in the protocol ([Section 6.3.4](#))
- Revised the range of study days for the Analysis Window and rules for handling data when multiple efficacy assessments fall within the same analysis window for an Analysis Visit ([Section 6.3.5](#))
- Clarified the LOCF approach to be used for the secondary efficacy endpoints in response to FDA's comments (dated November 3, 2021) on the final SAP v1.0 ([Sections 6.4.2 and 6.4.3.1](#))
- Included three iris color categories in the subgroup of iris color ([Section 6.4.7](#))
- Clarified missing data for "Observed-Case" sensitivity analysis of the primary endpoints ([Section 10.1.3](#))
- Revised the data handling rule from using the LOCF approach to using observed data for the Additional Analysis ([Section 10.1.4](#))
- Provided the definition of rescue medication use during the treatment period and clarified that only the first time of rescue medication use will be included in the analysis and summary when multiple rescue medications are used by a subject ([Section 10.2.2.3](#))
- Added the categories of the number of doses received per subject and revised the categories of treatment duration ([Section 11.1](#))
- Clarified only ocular adverse events will be summarized by relationship to both study drug and surgery, and then separately by relationship to surgery only ([Section 11.2](#))
- Clarified the use of BCVA Base LogMar score ([Section 11.3.2](#))

TABLE OF CONTENTS

Approval Signature Page	2
Summary of Changes in SAP Amendment 1	3
LIST OF TABLES	5
LIST OF FIGURES	5
List of Abbreviations	6
1. Introduction.....	7
2. Study Objectives and Endpoints.....	7

LIST OF FIGURES

Figure 1:	Study Schematic.....	9
------------------	-----------------------------	----------

LIST OF ABBREVIATIONS

Abbreviation	Definition
ACC	Anterior Chamber Cell
ACF	Anterior Chamber Flare
AE	Adverse Event
ANCOVA	Analyses of Covariance
ATC	Anatomical Therapeutic Chemical
BCVA	Best Corrected Visual Acuity
BID	Twice Daily
CI	Confidence Interval
CV	Coefficient of Variation
eCRF	Electronic Case Report Form
EOMS	End of Main Study
EOSS	End of Sub-Study
ETDRS	Early Treatment of Diabetic Retinopathy Study
IOP	Intraocular Pressure
ITT	Intent-to-Treat
LOCF	Last Observation Carried Forward
MedDRA	Medical Dictionary for Regulatory Activities
OD	Right Eye
OS	Left Eye
OU	Both Eyes
POD	Post-Operative Day
PP	Per-Protocol
SAE	Serious Adverse Event
SAP	Statistical Analysis Plan
SOC	System Organ Class
SUSAR	Serious and Unexpected Suspected Adverse Reaction
TEAE	Treatment-Emergent Adverse Event
WHO	World Health Organization

1. INTRODUCTION

This document is prepared in compliance with International Conference on Harmonization E9 and intended to provide details of statistical methodology and data handling rules to be used for the analyses of data from Protocol CPN-302 v1.2 (Amendment 1): A Multicenter, Randomized, Double-Masked, Placebo-Controlled, Parallel-Group Study to Evaluate the Efficacy and Safety of APP13007 for the Treatment of Inflammation and Pain after Cataract Surgery, Including a Corneal Endothelial Cell Sub-study. This Phase 3 study is being conducted in the United States.

2. STUDY OBJECTIVES AND ENDPOINTS

The study objectives and corresponding study endpoints are presented in [Table 1](#) below:

Table 1: Study Objectives and Endpoints

Objectives	Endpoints
Primary Efficacy Objective The primary efficacy objective is to investigate the efficacy of APP13007 versus matching vehicle placebo for the treatment of inflammation and pain through post-operative day (POD) 15 after cataract surgery in the study eye.	Primary Efficacy Endpoints 
• The proportion of subjects with Anterior Chamber Cell (ACC) Count = 0 [ACC Grade = 0] at post-operative day 8 (POD8), maintained through POD15• The proportion of subjects with Ocular Pain Grade = 0 at POD4, maintained through POD15
Secondary Efficacy Objective The secondary efficacy objective of this study is to investigate the effect of APP13007 versus matching vehicle placebo on markers of inflammation, ocular pain and visual acuity after cataract surgery in the study eye.	Secondary Efficacy Endpoints 
• Proportion of subjects with ACC count = 0 [ACC Grade = 0] at PODs 4, 8 and 15• Proportion of subjects with Ocular Pain Grade = 0 at PODs 4, 8 and 15• Proportion of subjects with Anterior chamber flare (ACF) Grade = 0 at POD8 maintained through POD15• Proportion of subjects with ACF Grade = 0 at PODs 4, 8 and 15• Mean change-from-baseline in ACC Grade at PODs 4, 8, and 15• Mean change-from-baseline in Ocular Pain Grade at PODs 4, 8 and 15• Mean change-from-baseline in ACF Grade on PODs 4, 8 and 15• Number of subjects rescued on or prior to each visit and overall• Mean change-from-baseline in best corrected visual acuity by pinhole method using an Early Treatment Diabetic Retinopathy Study (ETDRS) chart at PODs 4, 8 and 15

Objectives	Endpoints

Safety Objective
 
The safety objective is to investigate the safety and tolerability of APP13007 versus matching vehicle placebo for the treatment of inflammation and pain after cataract surgery.
	
Safety Endpoints
 
• Adverse events (AEs)• Best corrected visual acuity by pinhole method using an ETDRS chart from baseline to each post-surgery visit• Slit-lamp biomicroscopy
○ Change-from-baseline in ocular signs to each post-surgery visit• Dilated indirect ophthalmoscopy
○ Change-from-baseline in ocular signs to Visit 6 (POD22)• Mean changes in corneal endothelial cell density, percent hexagonality and coefficient of variation from baseline (Visit 1/Screening) to Visit 7 (POD85) in the study eye in subjects in the Endothelial Cell Sub-study• Intraocular pressure (IOP) at each visit and change-from-baseline to Visit 6 (POD22) measured with a Goldmann applanation tonometer

3. STUDY DESIGN

3.1 Study Design Overview

This Phase 3 study will evaluate APP13007 [REDACTED] in comparison to the matching vehicle placebo in a randomized, parallel-group, double-masked fashion. Subjects will have routine uncomplicated cataract surgery on Day 0 of the study and will be assessed the next day (POD1) after the surgery for eligibility for randomization to study treatment. The study comprises the Main Study and the Endothelial Cell Sub-study. All randomized subjects (approximately 370) will participate in the Main Study. The Endothelial Cell Sub-study will comprise a subgroup of approximately 176 subjects at study sites qualified to perform corneal endothelial cell parameter assessments.

All eligible subjects at the qualified study sites for corneal endothelial cell assessments will be requested to participate in the Sub-study. If a subject is unable or unwilling to participate in the Sub-study, the Investigator has the option to enroll the subject in the Main Study only, after consulting with the Study Medical Monitor.

Subjects who experience postoperative inflammation on POD1 and who meet all other eligibility criteria will be randomized, at a 1:1 ratio, to one of two study treatments (either Treatment 1 or Treatment 2):

[figure not shown]
- Treatment 1: 1 drop APP13007 twice daily (BID) (morning and evening) for 14 days instilled to the operated study eye
- Treatment 2: 1 drop matching vehicle placebo BID (morning and evening) for 14 days instilled to the operated study eye

After randomization, the first dose of study drug will be administered in the clinic on POD1 so that the site personnel can ensure the subject is able to administer the study drug correctly. The second drop of the study drug on POD1 will be administered by the subject a minimum of 6 hours later. For all other days, the first dose will be instilled in the morning and the second dose instilled a minimum of 6 hours, but preferably 8 to 12 hours, later. The number of drop(s) instilled and the date/time of instillation of each dose will be recorded by the subject in the subject's dosing diary. The study drug will be dosed BID for 14 days.

Any subjects who have evidence of persistent or worsening inflammation as described in the [protocol Section 9.4](#) may be rescued and placed on appropriate alternate therapy. The choice of rescue medication is at the Investigator's discretion. Rescued subjects will stop study drug and will not be withdrawn from the study. The rescued subjects will continue to be assessed at each subsequent visit, if possible, through completion of the Visit 6/POD22 assessments for the subjects in the Main study only or through completion of the Visit 7/POD85 assessments for the subjects in the Sub-study.

This study will include up to 7 scheduled clinic visits (including the surgery day) over a range of ~ 24 to ~ 51 days for the subjects in the Main Study who are not participating in the Endothelial Cell Sub-study, while subjects in the Endothelial Cell Sub-study will have up to 8 scheduled clinic visits (including the surgery day) over a range of ~ 87 to ~ 114 days ([Figure 1](#)). Subjects who are not participating in the Endothelial Cell sub-study will be discharged from the study after the assessments for Visit 6/POD22 have been performed. Subjects who are participating in the Endothelial Cell sub-study will be discharged from the study after the assessments for Visit 7/POD85 have been performed.

Figure 1: Study Schematic

3.2 Schedule of Events

All assessments including ocular assessments and safety assessments are outlined in Table 2.

Table 2: Schedule of Events

PROCEDURE/ASSESSMENTS ¹	Visit 1 Screening (Day -28 to -1)	Surgery ² Day 0	Visit 2 POD1 ³	Visit 3 POD4 (±1 Day)	Visit 4 POD8 (±1 Day)	Contact POD14	Visit 5 POD15 (+1 Day) ⁴	Visit 6 POD22 (±2 Days) ⁵	Reminders (~POD50 and ~POD78)	Visit 7 POD85 (±4 Days) ⁶
ICF, Demography, Medical History	X									
Determine Eligibility, Review Inclusion/Exclusion Criteria	X		X							
Urine pregnancy test only for women of child-bearing potential			X				X			
Ocular Symptoms Assessment ⁷	X		X	X	X		X	X		
ETDRS Visual Acuity	X		X	X	X		X	X		
Slit Lamp Biomicroscopy ⁸	X		X	X	X		X	X		
Indirect Ophthalmoscopy (dilated)	X								X	
IOP (Goldmann applanation tonometry) ⁹	X		X	X	X		X	X		
Corneal Endothelial Cell Parameters ¹⁰	X							X		X
Randomization				X						
Dispense Study Drug				X						
Study Drug Dosing BID for 14 days (POD1 to POD14) ¹¹				X	X	X	X			
Dispense Diary Card (with instructions for completion)				X	X	X				
Contact Subject ¹²						X			X	
Collect Study Drug							X			
Collect and Check Diary Cards for Accuracy and Compliance					X	X		X		
AEs ⁷ and Concomitant Medications ¹³	X	X ¹⁴	X	X	X	X ¹⁵	X	X		X ¹⁵

¹ Ophthalmic assessments will be performed in the study eye only at Visits 2-5 and Visit 7 and performed on both eyes at Visit 1 (Screening) and at Visit 6 (POD22) or at subject Early Termination/Withdrawal. In the Endothelial Cell Sub-study, corneal endothelial cell parameters are measured in both eyes at Screening and in the study eye only at Visit 6 (POD22) and Visit 7 (POD85).

² Surgery must occur between one to 28 days after Screening, preferably in the morning. If, due to unexpected events, surgery is postponed and would occur > 28 days past the Screening visit, contact the Study Medical Monitor to determine which, if any, of the screening procedures should be repeated. Subjects will be determined to be a suitable candidate for surgery during a pre-surgery medical assessment, where the routine medication list prescribed by the cataract surgeon should be reviewed to rule out prohibited medications ([protocol Section 5.4.2](#)).

³ Visit 2 (POD1) should be scheduled between 18 to 34 hours following conclusion of surgery on Day 0. All assessments done on POD1 are done prior to Randomization to ensure eligibility. Note: Women-of-childbearing-potential are eligible for enrollment if they have a negative urine pregnancy test on POD1 prior to Randomization and they agree to abstinence from sexual activity or use of highly effective method of contraception from POD1 to Visit 6 (POD22).

⁴ Visit 5 (POD15) occurs on the day after the subject completes the study drug administration for 14 days. Women-of-childbearing-potential should have a urine pregnancy test.

⁵ Visit 6 (POD22) is the last visit for subjects participating in the Main Study only. Subjects who are withdrawn early should have the Visit 6 assessments and a urine pregnancy test, if applicable, performed before they are released from the study.

⁶ Visit 7 (POD85) is the last visit for subjects participating in the Endothelial Cell Sub-study.

⁷ Includes assessments of ocular pain and irritation. See [protocol Section 8.0](#) for information on how to record AEs and how to determine attributability (relatedness) of AE to study procedures (including cataract surgery) or study drug.

⁸ Ocular inflammation assessment using ACC count, anterior chamber flare grade, bulbar conjunctival injection, sclera - ciliary flush and corneal edema.

⁹ IOP should (but not required) be assessed at each visit within ± 2 h of the IOP assessment time at Visit 1.

¹⁰ Only performed in the subjects in the Endothelial Cell Sub-study at participating centers. The parameters are: endothelial cell density (cells/mm²), percent hexagonality and coefficient of variation. Performed in both eyes at the Screening visit and in the study eye at Visit 6 (POD22) and Visit 7 (POD85).

¹¹ The first dose of study drug should be instilled into the study eye at the clinic visit under supervision of clinic staff. The second dose on POD1 can be administered at home. Subjects who are rescued will not continue to instill study drug or receive further diary cards but will remain in the study to complete the procedures/assessments through Visit 6 (POD22) (Main Study) or Visit 7 (Endothelial Cell Sub-study).

¹² The site must contact the subject via the subject's preferred method on POD14 to remind him/her not to instill study drug on POD15 and to bring the bottle of study drug and the dosing diary back to the site at the POD15 visit. In addition, the subjects in the Endothelial Cell Sub-study will be sent US mail/email/voicemail/text message reminders on ~POD50 and ~POD78 to return for Visit 7 (POD85).

¹³ Concomitant medications used for rescue should be reported in the eCRF.

¹⁴ AEs and Concomitant Medications should only be recorded on Day 0 if they result in disqualification (i.e., screen failure) of the subject; otherwise, the AEs and Concomitant Medications applicable to Day 0 should be recorded when the subject returns for Visit 2 (POD1).

¹⁵ Any AEs reported to the site during the POD14 contact or as a result of the POD50/POD78 reminders must be recorded in the source documents. Further assessment of any reported AEs may require an Unscheduled Visit if medically significant or they may be assessed, as appropriate, during Visit 5 (POD15) or Visit 7 (POD85), respectively.

4. SAMPLE SIZE CONSIDERATION

The assumption for the sample size determination was estimated using the Package Inserts of Durezol®, Lotemax® and Inveltys® and results from the APP13007 Phase 2 study (CPN-201). The sample size for the ACC count primary efficacy endpoint is based on the assumption of 26% of subjects in APP13007 group with ACC Count = 0 at POD8 and maintained through POD15 and 12% of subjects in the matching vehicle placebo group. The two-group Chi-square test, with a two-sided significance level of 5% and 92% power, requires 175 subjects per treatment group to detect the difference between APP13007 and placebo.

The same sample size using the assumption of 57% of subjects with Ocular Pain Grade = 0 at POD4 and maintained through POD15 in APP13007 group and 38% of subjects in the placebo group will provide 95% power to detect the treatment difference.

With an estimated 5% dropout rate, this study will randomize approximately 185 subjects per treatment group for a total of approximately 370 subjects.

In the Endothelial Cell Sub-study, a sample size of 80 subjects per treatment group is considered adequate to evaluate the corneal endothelial cell parameters between treatment groups. With a 10% dropout rate, the Sub-study will enroll approximately 88 subjects per treatment group for a total of approximately 176 subjects to be randomized for the Endothelial Cell Sub-study.

5. ANALYSIS POPULATIONS

The analysis populations are defined below.

5.1 Intent-to-Treat (ITT) Population

The ITT population will consist of all subjects who are randomized to the study drug.

Following the ITT principle, subjects will be analyzed according to the treatment assignment at randomization.

5.2 Per-protocol (PP) Population

The PP population will consist of all subjects in the ITT population who (i) receive at least 1 dose of study drug, (ii) do not have major protocol deviations that would impact the evaluation of efficacy, and (iii) have at least 80% overall treatment compliance.

The subjects who are to be excluded from the PP population will be identified prior to database lock and unmasking of the treatment assignment and the reason for exclusion will be documented and listed.

5.3 Safety Population

The safety population will consist of all randomized subjects who receive at least one dose of study drug.

Subjects will be analyzed in the safety analysis according to the treatment actually received.

6. DATA ANALYSIS CONSIDERATIONS

6.1 General Consideration

All statistical analyses and generation of tables, figures, subject data listings, and statistical output will be performed using SAS Version 9.3 or higher.

6.2 General Presentation of Summaries and Analyses

Descriptive statistics will be displayed to provide an overview of the study results. For categorical variables, the number and percentage of subjects in each category will be presented. Unless otherwise noted, all percentages will be displayed to 1 decimal place. No percentage will be displayed for zero counts, and no decimal will be presented when the percentage is 100%. For continuous variables, descriptive statistics will include number of subjects with available measurements (n), mean, standard deviation, median, first quartile (Q1), third quartile (Q3), minimum, and maximum.

Decimal places for descriptive statistics will apply the following rules unless otherwise stated:

- “n” will be an integer
- Mean, standard deviation, and median will use one additional decimal place compared to the original value
- Minimum and maximum will have the same number of decimal places as the original value

Continuous variables will be examined to ensure that they meet the required assumptions for the intended statistical analysis method. If the statistical assumptions are violated, alternative analytical methods, such as nonparametric statistics, will be used.

Unless otherwise specified, all statistical tests will be two-sided and the statistical significance will be tested at the 5% level ($\alpha = 0.05$). Statistical tests of efficacy variables will be presented as two-sided p-values rounded to three decimal places. P-values less than 0.001 will be presented as “<0.001” and p-values greater than 0.999 will be presented as “>0.999”.

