6.4.6 Multiple Comparisons/Multiplicity

Since the comparisons of the primary efficacy endpoints will be performed in the pre-specified sequential order, the fixed-sequence hierarchical testing approach will be used to adjust for multiple comparisons. These endpoints will be tested in the sequence with the rule that once a

p-value exceeds 0.05, the endpoint further down in the sequence will not be claimed for statistical significance.

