10.2 Analyses of Secondary Efficacy Endpoints

10.2.1 Secondary Efficacy Endpoints

The secondary efficacy endpoints are:

- Proportion of subjects with ACC count = 0 (ACC grade = 0) at PODs 4, 8 and 15
- Proportion of subjects with Ocular Pain grade = 0 at PODs 4, 8 and 15
- Proportion of subjects with ACF grade = 0 at POD8 maintained through POD15
- Proportion of subjects with ACF grade = 0 at PODs 4, 8 and 15
- Mean change from baseline in ACC grade at PODs 4, 8, and 15
- Mean change-from baseline in Ocular Pain grade at PODs 4, 8 and 15
- Mean change from baseline in ACF grade on PODs 4, 8 and 15
- Number of subjects rescued on or prior to each visit and overall
- Mean change from baseline in best corrected visual acuity (BCVA) by pinhole method using an ETDRS chart at PODs 4, 8 and 15

The ACC count and Ocular Pain grade will be graded using the same grading scale described for primary efficacy endpoints ([Section 10.1.1](#)).

The ACF will be graded as follow:

Grade	Description
0	None
1	Faint
2	Moderate (iris and lens details clear)
3	Marked (iris and lens details hazy)
4	Intense (fibrin or plastic aqueous)

Subjects who meet the rescue criteria may be rescued and placed on an appropriate alternative therapy as determined by the Investigator. The rescue criteria are provided in the [protocol Section 9.4](#).

The ETDRS visual acuity (logMAR score) will be calculated as follows using Original EDTRS Chart 1 and Chart 2:

1. Determine the last row where the subject can correctly identify at least one (1) letter in that row. This is the base logMAR line.
2. Determine the log score for the base logMAR line.
3. Add 0.02 ($T = 0.02$) log units for every letter that is incorrectly identified up to and including the base logMAR line.

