10.2.2 Analysis of Secondary Efficacy Endpoints

10.2.2.1 Analysis of Categorical Endpoints of ACC, Ocular Pain and ACF

The secondary efficacy endpoints (categorical endpoints) of ACC grade, Ocular Pain grade and ACF grade will be analyzed and summarized in the same manner as described for the primary efficacy endpoints ([Section 10.1.2](#)). The imputation for missing values for the categorical endpoints is described in [Section 6.4.3.1](#). The proportion of subjects with ACC grade = 0, Ocular Pain grade = 0, and ACF grade = 0 at PODs 4, 8, and 15 will be plotted separately for each of these endpoints.

In addition, the ACC grade, Ocular Pain grade and ACF grade will be tabulated, including the number and percentage of subjects in each grade category, using the observed data only.

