10.2.2.3 Analysis of Endpoint of Rescue Medication Use

The overall number of subjects rescued during the treatment period will be compared between treatment groups using the Pearson Chi-square test. “Rescued during treatment period” is defined as use of rescue medications during the 14-day study drug treatment period. When the treatment duration of study drug is < 14 days, use of rescue medications will be excluded from the analysis when rescue medications are started > 2 days after the last dose of study drug.

In addition, the cumulative number of subjects rescued at PODs 4, 8, and 15 will be summarized by treatment group and compared between treatment groups using the Pearson Chi-square test at each Analysis Visit. In addition, the number and percentage of subjects rescued in each category of criteria for rescue will be presented for the overall study and at PODs 4, 8, and 15. If multiple rescue medications are used by a subject, only the first time a rescue medication is used will be included in the analysis and summary.

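### Twenty-six secondary comparisons are tested at two-sided 5% with no multiplicity control and no condition on the primary endpoints

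*SAP*

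**What the plan says.** The default is in SAP 6.2: "Unless otherwise specified, all statistical tests will be two-sided and the statistical significance will be tested at the 5% level". Protocol 10.5 repeats it.

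Multiplicity is handled in SAP 6.4.6, whose scope is set by its opening clause: "Since the comparisons of the primary efficacy endpoints will be performed in the pre-specified sequential order". SAP 10.1.2 and protocol 10.3.2.1 give the order, ACC count = 0 sustained from POD8 and then pain grade = 0 sustained from POD4. No third member is named.

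The secondary comparisons are set out in SAP 10.2.1 to 10.2.2.3:

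- Responder endpoints: clearance of cells, of pain and of flare, each judged separately at the three analysis visits, and a sustained flare endpoint, "Proportion of subjects with ACF grade = 0 at POD8 maintained through POD15". SAP 10.2.2.1 says these "will be analyzed and summarized in the same manner as described for the primary efficacy endpoints".
- ANCOVA of change from baseline in ACC grade, pain grade, flare grade and BCVA at three visits (10.2.2.2).
- Rescue (10.2.2.3): a chi-square test overall, and cumulative numbers "compared between treatment groups using the Pearson Chi-square test at each Analysis Visit".

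Elsewhere the SAP does limit inference. Section 6.4.5 calls a possible site-adjusted analysis exploratory, and 6.4.7 rules out statistical comparisons in subgroups. The secondary endpoints carry no such limit.

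**The concern.** Because the 5% rule applies wherever nothing else is specified, it governs all the secondary tests. The stop rule in SAP 6.4.6 and 10.1.2 acts only on a later endpoint in the sequence, and the sequence has two members.

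The result is inconsistent. If the ACC test fails, sustained pain relief cannot be claimed, yet pain grade = 0 at POD4, POD8 or POD15 could still be called significant at 5%. The same holds for flare, visual acuity and rescue. At stake is how much weight a reader may put on a secondary p-value below 0.05. BCVA is the clearest case: it is a named secondary efficacy endpoint that neither primary implies, and it gets three unadjusted tests.

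**Working it through.** **The plan's own figures.** The documents state no error rate for the secondary family, so there is none to reproduce. The sample-size statement (SAP 4) does check out: 175 per group gives 91.9% power for 26% vs 12% and 94.8% for 57% vs 38%, against the stated 92% and 95%. The point does not depend on these.

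**Count of tests (SAP 10.2.1 to 10.2.2.3).**

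- ACC, pain and flare grade = 0 at three visits: 3 × 3 = 9
- Sustained flare grade = 0: 1
- ANCOVA, four variables at three visits: 4 × 3 = 12
- Rescue, three visits plus overall: 3 + 1 = 4
- Total: 9 + 1 + 12 + 4 = 26

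Overall rescue in the treatment period and cumulative rescue at POD15 are nearly the same comparison, so about 25 are distinct.

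**Expected false rejections if nothing works.** 26 × 0.05 = 1.3, whatever the correlation.

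**Chance of at least one, independent tests.**

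- Either direction: 1 − 0.95^26 = 73.6% (with 25 tests, 1 − 0.95^25 = 72.3%)
- In favor of APP13007, 2.5% per test: 1 − 0.975^26 = 48.2%

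**Allowing for correlation.** The tests share subjects, visits and scores, and the documents give no correlations. With 26 normal statistics at an assumed common correlation (200,000 runs each):

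| Common correlation | At least one, either direction | At least one favoring APP13007 |
|---|---|---|
| 0 | 74% | 48% |
| 0.2 | 67% | 37% |
| 0.3 | 62% | 33% |
| 0.4 | 55% | 28% |
| 0.5 | 47% | 24% |
| 0.7 | 32% | 16% |
| 0.9 | 17% | 8% |

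The two-sided figure crosses one half between 0.4 and 0.5.

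Two separate simulations of the 26 tests under no effect (370 subjects, 2,000 trials per setting) used assumed between-visit correlations of 0.3 to 0.7 and between-sign correlations of 0 to 0.5. Across both, the two-sided figure was 60-64%. In the one that also recorded direction, the figure favoring APP13007 was 33-36%.

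**BCVA alone.** Three independent tests give 1 − 0.95^3 = 14.3%. Simulation gave 12-13% in either direction. Three normal statistics with correlation 0.5 to 0.7 give 5.5-6.3% in favor of APP13007, against 2.5% for a single test.

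**Would a gate suffice?** If nothing works, requiring both primaries to succeed first would cap the favorable error at about 2.5%. If the ACC and pain effects are real, the gate opens and no longer protects. As an illustration, suppose flare (3 responder + 1 sustained + 3 ANCOVA = 7 tests) and BCVA (3 tests) are unaffected. The chance of at least one false rejection among these 10, if independent, is 1 − 0.95^10 = 40%, or 1 − 0.975^10 = 22% in favor of APP13007.

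**The case against.** The strongest reply is that secondary analyses are commonly read as supportive, and the documents never say their p-values will support claims. The wording about claiming significance appears only in the primary sequence, and nothing proposes promoting secondaries after a failed primary. That is a fair limit on what can be inferred about intent. It does not remove the rule in SAP 6.2, which provides for significance testing and not merely the display of p-values.

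Second, the global null is a narrow scenario. Where the primary effects are real, the visit-level ACC and pain tests largely break down the primary result and are not fresh chances of error. This stands, and it is why flare, BCVA and rescue matter more than the total of 26.

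Third, SAP 10.2.2.1 might be thought to carry the hierarchy over to the secondaries. It cannot, because no order of secondaries is defined, and the section covers only the categorical grade endpoints, not ANCOVA, BCVA or rescue.

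Fourth, part of the remedy is already there. Treatment differences with 95% confidence intervals are planned for the categorical secondaries (SAP 10.1.2 through 10.2.2.1) and for the ANCOVA endpoints (10.2.2.2). This stands; only the rescue comparisons lack one.

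**Conclusion.** The gap is real and follows from a stated rule: 26 secondary comparisons, about 25 distinct, each at two-sided 5%, unadjusted and not conditional on the primaries. The count and the expected 1.3 false rejections need only the SAP and the assumption of no effect. The probability of at least one rests on correlations that the documents do not give: up to 74% if independent, 60-64% in the assumed moderate settings, and below 50% at a common correlation of about 0.5 or more.

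A reader might infer that a false-positive efficacy claim is more likely than not. The documents do not support that. The higher figures count rejections in either direction, including those favoring placebo. In favor of APP13007 the chance is about 48% under independence, lower with the positive correlation expected here, and 33-36% in simulation. It is below one half throughout, though still far above the 2.5% that the primary sequence allows. Nor is the primary result in doubt, since the fixed sequence protects the type I error of both primary endpoints. The consequence is confined to how secondary results may be described.

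**What to change.** In SAP 6.2 and 6.4.6 and protocol 10.5, limit the 5% significance statement to the two primary endpoints in the fixed sequence. State that all secondary comparisons are reported with 95% confidence intervals and p-values labelled nominal, and add an interval for the treatment difference in rescue to SAP 10.2.2.3.

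A confirmatory secondary hierarchy is optional and the sponsor's choice. If any secondary claim is wanted, for example BCVA, continue the fixed sequence after both primaries succeed through a short pre-specified list, naming the visit for each endpoint. A gate without an order or an alpha split is not enough. Bonferroni over all 26 would also control the error, but at 0.05/26 = 0.0019 per test.

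The cost is about one SAP paragraph and a matching protocol sentence, with no new data or subjects. The downside is that fewer secondary results can be called significant.
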